5.5.4 Instructions for prescribing and taking study treatment

All patients will receive Secukinumab 300 mg subcutaneously using the Phase III regimen: 300 mg (two 150 mg injections) a week for the first five weeks (visits 3-7), and once every 4 weeks thereafter (visits 8-12). Patients proceeding to the extension period will self-administer treatment (two 150 mg injections) once every 4 weeks for an additional 48 weeks.

The study treatment solution must be injected subcutaneously in non-affected areas of the skin.

Following the evaluation of psoriasis severity at 16 weeks, patients achieving a PASI 50 response will be eligible to continue on the study treatment for another 8 weeks. Their PASI score will be evaluated at 24 weeks. Willing patients reaching at least a PASI 75 response at the end of the 24-week core study will enter an extension treatment period of an additional 48 weeks.

All dates of injections given to the subject during the study must be recorded on the Dosage Administration Record e-CRF.

5.5.5 Permitted dose adjustments and interruptions of study treatment

Investigational treatment dose adjustments and/or interruptions are not permitted.

5.5.6 Rescue medication

The investigator may prescribe any medications and/or supportive care during the study based on clinical needs. Use of rescue medication must be recorded on the Concomitant medications/Significant non-drug therapies/Dose Administration Record in the Electronic Case Report Form (eCRF).

5.5.7 Concomitant treatment

The investigator should instruct the patient to notify the study site about any new medications he/she takes after being enrolled into the study. All medications, procedures and significant non-drug therapies (including physical therapy and blood transfusions) administered after the patient was enrolled into the study must be recorded.

5.5.8 Prohibited Treatment

Use of the treatments displayed in [Table 5-1](#) is NOT allowed after screening.

If a prohibited treatment listed in [Table 5-1](#) is used during the study, the patient must discontinue use of the prohibited treatment if he/she wishes to continue in the study. At the discretion of the investigator, if the patient's use of a prohibited treatment presents undue safety risk for the patient, he/she should be discontinued from study treatment as per [Section 5.5.9](#). If the patient receives a live virus vaccination during the study, he/she must discontinue study treatment and enter the post-treatment follow up period.

Table 5-1: Prohibited treatment

Prohibited treatments	Washout period (before day 1)
Secukinumab or any other biologic drug directly targeting IL-17 or the IL-17 receptor	No prior use allowed
Ustekinumab	No prior use allowed
Alefacept, briakinumab, efalizumab	6 months
Biological immunomodulating agents other than the above:	
Etarnecept	3 weeks
Adalimumab	6 weeks
Infliximab	12 weeks
Golimumab	8 weeks
Other systemic immunomodulating treatments [e.g., MTX, cyclosporine A, corticosteroids (oral, i.v., intramuscular, s.c., intra-articular, transdermal), cyclophosphamide]	4 weeks
Other systemic psoriasis treatments (e.g. retinoid, fumarates)	4 weeks
Photo chemotherapy (e.g. PUVA)	4 weeks
Phototherapy (e.g., UVA, UVB)	2 weeks
Topical treatment that is likely to impact signs and symptoms of psoriasis (e.g. vitamin D analogues, pimecrolimus, retinoids, salicylvaseline, salicylic acid, lactic acid, tacrolimus, tar, urea alpha-hydroxy or fruit acids)	2 weeks

Live virus vaccinations	6 weeks
Any investigational treatment or participation in any interventional trial	4 weeks or 5 half-lives (whichever is longer)
Prohibited regimen of Topical Corticosteroids (TCS):	
TCS higher than moderate potency on any body location	2 weeks
TCS mild to moderate potency on any body location other than the face, scalp and or genitoanal area	2 weeks
TCS mild to moderate potency on the face, scalp and or genitoanal area	1 day

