Biological agents	A substance that is made from a living organism or its products and is used in the prevention, diagnosis, or treatment of cancer and other diseases. Biological drugs include antibodies, interleukins, and vaccines.
Cohort	A group having one or more similar characteristics (such as habit of smoking or a particular disease) closely monitored over time.
Human Leukocyte Antigen	A collection of human genes on chromosome 6 that encode proteins that function in cells to transport antigens from within the cell to the cell surface. These proteins are sometimes referred to as the MHC, or major histocompatibility complex.
Interleukin	Any of a class of glycoproteins produced by leukocytes for regulating immune responses.
Investigational treatment	All investigational drugs whose properties are being tested in the study as well as their associated treatment controls. This includes any placebos, any active controls, as well as approved drugs used outside of their indication/approved dosage or tested in a fixed combination. Investigational treatment generally does not include other treatments administered as concomitant background therapy required or allowed by the protocol when used within approved indication/dosage.
Monoclonal Antibody	An antibody produced by a single clone of cells. A monoclonal antibody is therefore a single pure type of antibody. Monoclonal antibodies can be made in large quantities in the laboratory and are a cornerstone of immunology. Monoclonal antibodies are increasingly coming into use as therapeutic agents.
Phase IIIb study	Clinical trials conducted after regulatory submission of a dossier, but prior to the medicine's approval and launch. These trials may supplement earlier trials, complete earlier trials, or may be directed toward new types of trials (e.g., quality of life, marketing) or Phase IV evaluations. This is the period between submission and approval of a regulatory dossier for marketing authorization.
Premature patient withdrawal	Point/time when the patient exits from the study prior to the planned completion of all investigational/study treatment administration and all assessments (including follow-up).
Study/investigational treatment discontinuation	Point/time when patient permanently stops taking study/investigational treatment for any reason; may or may not also be the point/time of premature patient withdrawal.

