5.5.9 Discontinuation of study treatment and premature patient withdrawal

Patients may voluntarily withdraw from the study for any reason at any time. They may be considered withdrawn if they state an intention to withdraw, fail to return for visits, or become lost to follow-up for any other reason.

If premature withdrawal occurs for any reason, the investigator must make every effort to determine the primary reason for a patient's premature withdrawal from the study and record this information.

The investigator should discontinue the investigational treatment for a given patient and/or withdraw the patient from the study if, on balance, he/she believes that continuation would be detrimental to the patient's well-being.

The investigational treatment must be discontinued under the following circumstances:

- Withdrawal of informed consent
- Severe adverse events that, in the opinion of the Investigator, warrant discontinuation
- Pregnancy
- Use of prohibited treatment as per [Table 5-1](#)
- Any other protocol deviation that results in a significant risk to the patient's safety

Patients that do not achieve PASI 50 at week 16 will terminate treatment. For patients who are lost to follow-up (i.e. those patients whose status is unclear because they fail to appear for study visits without stating an intention to withdraw), the investigator should show "due diligence" by documenting the steps taken to contact the patient, e.g. dates of telephone calls, registered letters in the source, etc.

Patients who are prematurely withdrawn from the study will not be replaced by an equal number of newly enrolled patients.

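### Protocol 5.5.8 and 5.5.9 disagree on whether secukinumab must stop after a prohibited treatment, so sites may handle the same event differently

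*Protocol*

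**What the plan says.** **Protocol 5.5.8** bars Table 5-1 treatments after screening and then says what happens if one is used:

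- General rule: "the patient must discontinue use of the prohibited treatment if he/she wishes to continue in the study".
- Stopping secukinumab is left to the investigator's discretion: "if the patient's use of a prohibited treatment presents undue safety risk for the patient, he/she should be discontinued from study treatment", with a reference to 5.5.9.
- One mandatory case: "If the patient receives a live virus vaccination during the study, he/she must discontinue study treatment and enter the post-treatment follow up period".

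**Protocol 5.5.9** opens its list with "The investigational treatment must be discontinued under the following circumstances". One item is "Use of prohibited treatment as per" Table 5-1. It carries no safety condition, no discretion and no exception for a patient who stops the prohibited treatment. A separate item does carry a safety condition: "Any other protocol deviation that results in a significant risk to the patient's safety".

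**Protocol 5.5.6** (rescue medication) says "The investigator may prescribe any medications and/or supportive care during the study based on clinical needs" and does not mention Table 5-1.

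**SAP 2.4.2** names methylprednisolone, acitretin and a topical cream, given for reasons such as worsening psoriasis, as the study's rescue medication. **SAP 2.11** (resource utilization) describes costing of rescue medication and gives methotrexate and corticosteroids as the drugs.

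**The concern.** The same event, use of a Table 5-1 treatment during the study, leads to two outcomes. Under 5.5.8 a patient who stops the prohibited treatment may stay on secukinumab unless the investigator sees undue risk. Under 5.5.9 secukinumab stops. 5.5.8 refers the reader to 5.5.9 for the discontinuation, so a site that follows the reference meets a stricter rule than the one it came from.

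About 50 centres are planned, and nothing in either document says which section prevails. What is at stake is the meaning of the PASI values recorded afterwards. For an event before week 16, the primary PASI 90 result may be measured on secukinumab in one centre and off it in another. Visits up to week 72 are affected in the same way, as are the counts of treatment discontinuation by cohort.

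**Working it through.** No arithmetic bears on this point. The check is a comparison of the passages.

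**1. The two rules side by side**

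| Event | Protocol 5.5.8 | Protocol 5.5.9 | Consistent? |
|---|---|---|---|
| Table 5-1 treatment used, then stopped, no undue risk seen | Patient may continue | Secukinumab must stop | No |
| Table 5-1 treatment used, undue risk seen | Secukinumab should stop, at the investigator's discretion | Secukinumab must stop | Same direction, different force |
| Live virus vaccination | Secukinumab must stop | Secukinumab must stop | Yes |

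**2. Can continuing in the study mean follow-up off drug?** The glossary says that stopping treatment "may or may not also be the point/time of premature patient withdrawal", and Protocol section 6 asks patients off drug to return for the Table 6-1 assessments. That reading would remove the conflict, but 5.5.8 does not bear it. If every Table 5-1 use already stopped secukinumab, the sentence that makes stopping depend on undue risk would have no content. Nor would there be any need for a separate mandatory stop after live vaccination. A pause is not a middle course either, because 5.5.5 does not permit interruptions.

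**3. Is the overlap practical?** Table 5-1 lists methotrexate and systemic corticosteroids among prohibited immunomodulators, and retinoids among prohibited systemic psoriasis treatments. The SAP treats methylprednisolone and acitretin as rescue medication and expects to cost methotrexate and corticosteroids as rescue. The SAP gives no route for methylprednisolone; it falls under this Table 5-1 entry if given systemically. So drugs that the SAP expects as rescue are also drugs on which 5.5.8 and 5.5.9 disagree.

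**4. What changes in the analysis?**

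- *ITT, week 16.* SAP 2.5.3 applies LOCF to patients who leave the study prematurely or miss visits, and NRI to missing responses. The sensitivity analysis in SAP 2.5.4 concerns patients who left without a week-16 PASI. None of these rules addresses a PASI that is observed after a prohibited treatment. Under 5.5.8 that value is on secukinumab, possibly helped by the other therapy. Under 5.5.9 it is off secukinumab but still observed if the patient attends.
- *PP.* SAP 5.5, Table 1, excludes concomitant ustekinumab, alefacept, etanercept, adalimumab and phototherapy (COMD02, 04, 06, 08, 14). It also excludes other systemic immunomodulators, other systemic psoriasis treatments and topical treatments (COMD17, 18, 19). These patients leave the PP set whichever protocol section the site follows. COMD10 and COMD12 appear in the SAP 2.3 note on concomitant use but not in its major-deviation list or in Table 1. For those two codes PP status may still depend on whether the patient is recorded as completing the study.
- *Disposition.* Under 5.5.9 each such patient is a treatment discontinuation; under 5.5.8 not necessarily.

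**The case against.** Four arguments limit the point.

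*A patient stopped under 5.5.9 is not a dropout.* A reader might infer that the choice of section moves the patient between an observed response, an imputed value and PP exclusion. The documents do not support this. Stopping treatment is distinct from leaving the study, patients off drug are asked to return, and LOCF and NRI act only on missing data. PP exclusion mostly follows under both sections. This argument stands in full; what remains is on-drug versus off-drug exposure and disposition.

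*5.5.6 is a general permission beside a specific prohibition.* The two can be read together, with Table 5-1 limiting what may be prescribed. This is fair, and 5.5.6 alone would be weak evidence. The SAP rescue list shows that the overlap is nevertheless real.

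*Differing practice is a forecast.* The documents show that sites may act differently, not that they will.

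*Cw6 status is blinded to patients and investigators.* Sites therefore cannot choose their handling by known cohort. That argues against deliberate bias between cohorts but does not remove the inconsistency.

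None of these arguments reconciles 5.5.8 with 5.5.9.

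**Conclusion.** The conflict is real and can be read directly from the text. Protocol 5.5.8 and 5.5.9 give incompatible instructions on secukinumab for every Table 5-1 treatment except live virus vaccination. The main consequence is that PASI values after a prohibited treatment, including week 16 in the ITT analysis, may be observed on or off secukinumab depending on which section a site follows. Disposition counts vary with it.

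The size cannot be determined: neither document gives the frequency or timing of prohibited treatment. It is tempting to quote 1/146 = 0.7 percentage points against the 12-point margin. That is only the weight of one evaluable Cw6-negative patient whose response status changes. It is not an estimate of bias, and a change of section need not change the response.

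The conclusion about ITT rests on SAP 2.2 and on Table 1 of SAP 5.5, which remove these deviations from PP only. Table 2 of SAP 5.5, read literally, also lists severity code 4 among the ITT exclusions, and these deviations carry that code. The SAP should settle this too.

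**What to change.** - **Protocol.** Reconcile 5.5.8 and 5.5.9 so that one rule governs secukinumab after use of a Table 5-1 treatment, and cross-refer 5.5.6 to Table 5-1. Which rule applies is a clinical decision for the sponsor; this review does not propose one.
- **SAP.** State how a PASI observed after a prohibited treatment enters the week-16 ITT analysis and later visits, in line with the reconciled rule. This sentence would be needed even if the two protocol sections already agreed. Settle the status of COMD10 and COMD12, and the Table 1 and Table 2 codes in SAP 5.5, at the same time.
- **Reporting.** For patients already affected, tabulate by cohort whether secukinumab was continued or stopped after the prohibited treatment, and whether this happened before week 16.

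The cost is a written protocol amendment with the approvals required by Protocol 11.1, a short SAP addition and one table. The sample size does not change, and no new assessments are needed.

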5.5.9 Discontinuation of study treatment and premature patient withdrawal

Patients may voluntarily withdraw from the study for any reason at any time. They may be considered withdrawn if they state an intention to withdraw, fail to return for visits, or become lost to follow-up for any other reason.

If premature withdrawal occurs for any reason, the investigator must make every effort to determine the primary reason for a patient's premature withdrawal from the study and record this information.

The investigator should discontinue the investigational treatment for a given patient and/or withdraw the patient from the study if, on balance, he/she believes that continuation would be detrimental to the patient's well-being.

The investigational treatment must be discontinued under the following circumstances:

- Withdrawal of informed consent
- Severe adverse events that, in the opinion of the Investigator, warrant discontinuation
- Pregnancy
- Use of prohibited treatment as per [Table 5-1](#)
- Any other protocol deviation that results in a significant risk to the patient's safety

Patients that do not achieve PASI 50 at week 16 will terminate treatment. For patients who are lost to follow-up (i.e. those patients whose status is unclear because they fail to appear for study visits without stating an intention to withdraw), the investigator should show "due diligence" by documenting the steps taken to contact the patient, e.g. dates of telephone calls, registered letters in the source, etc.

Patients who are prematurely withdrawn from the study will not be replaced by an equal number of newly enrolled patients.

5.5.10 Emergency breaking of treatment assignment

Not applicable.

5.5.11 Study completion and post-study treatment

The core study will have a duration of 24 weeks. Following the evaluation of psoriasis severity at week 16, patients achieving PASI 50 response will be eligible to continue on the study treatment for an additional 8 weeks. Willing patients reaching at least a PASI 75 response during the core study will be eligible to enter an extension treatment period of an additional 48 weeks.

The investigator must provide follow-up medical care for all patients who are prematurely withdrawn from the study, or must refer them for appropriate ongoing care.

5.5.12 Early study termination

The study can be terminated at any time for any reason by Novartis. Should this be necessary, the patient should be seen as soon as possible and treated as a prematurely withdrawn patient. The investigator may be informed of additional procedures to be followed in order to ensure that adequate consideration is given to protect the patient's interests. The investigator will be responsible for informing Ethics Committees (ECs) of the early termination of the trial.

The study extension can be terminated by Novartis for any reason after a period of at least 12 weeks. Termination may occur only in selected regions where the drug is commercially available; this decision will be made on a region-by-region basis, as for some regions the study will continue as planned even though secukinumab may have become commercially available.

6 Visit schedule and assessments

Table 6-1 lists all of the assessments and indicates with an "x" when the visits are performed. All data obtained from these assessments must be supported in the patient's source documentation.

Patients should be seen for all visits on the designated day. A time window of ± 2 days for weekly visits and ± 7 days for the monthly visits is allowed.

Patients who discontinue the investigational treatment should also return for the assessments in Table 6-1. If they refuse to return for these assessments or are unable to do so, every effort should be made to contact them or a knowledgeable informant by telephone, reporting it in the source documents.

At a minimum, patients will be contacted for safety evaluations during the 30 days following the last study visit, including a final contact at the 30-day point. Documentation of attempts to contact the patient should be recorded in the source documentation.

Table 6-1: Assessment schedule (core study)

Visit	1	2	3	4	5	6	7	8	9	10	11	12/EoS
Week (relative to baseline)	-4	-2	0 (± 2 days)	1 (± 2 days)	2 (± 2 days)	3 (± 2 days)	4 (± 2 days)	8 (± 7 days)	12 (± 7 days)	16 (± 7 days)	20 (± 7 days)	24 (± 7 days)
Day	-28	-14 to -7	1	7	14	21	28	56	84	112	140	168
Informed consent	X											
Demographic data		X										
Inclusion/Exclusion criteria		X	X									
Smoking history		X										
Medical History		X										
TNF α - 308 polymorphism	X											
Psoriasis: medical history		X										
Previous Psoriasis therapies		X										
Quantiferon TB-Gold (within 3 months)		X										
Physical Examination		X	X	X	X	X	X	X	X	X	X	X
Height, weight, BMI and waist		X	X							X		X
Vital signs		X	X				X	X	X	X	X	X
PASI		X	X	X	X	X	X	X	X	X	X	X
IGA mod 2011		X	X	X	X	X	X	X	X	X	X	X
Lab assessments: hematology and chemistry ¹		X	X				X	X	X	X	X	X
hsCRP			X							X		X
HCV, HBV* and HIV tests (within 6 months)		X										
Serum pregnancy test		X										
Urinalysis		X								X		X
Secukinumab administration			X	X	X	X	X	X	X	X	X	X
DLQI			X							X		X
HADS			X							X		X
Cw6 centralized determination	X											
ECG (within 6 months)		X										
Chest X-ray (within 6 months)		X										
Study completion												X [^]
Concomitant medication												As needed
Adverse events												As needed
Liver events												As needed

¹Hematology: Hemoglobin, hematocrit, red blood cell count, white blood cell count with differential (e.g. neutrophils, basophils, eosinophils, monocytes, lymphocytes) and platelet count; Chemistry: Albumin, alkaline phosphatase, total bilirubin, bicarbonate/CO₂, calcium, cholesterol, chloride, creatinine, CK, GGT, glucose, LDH, inorganic phosphorus, lipase, amylase, magnesium, potassium, total protein, AST, ALT, sodium, triglycerides, urea/BUN and uric acid.

* Height will be assessed only at screening or at baseline

* HBsAg, HBsAb, HBcAb

[^] End of Study visit for patients not proceeding to the extension treatment period.

Table 6-2 lists all the assessments of the extension phase and indicates with an “x” when the visits are performed.

Patients should be seen for all visits on the designated day but a time window of ± 7 days is allowed.

Table 6-2: Assessment schedule of extension treatment period

Visit	E0*	E1	E2	E3	E4/ End of Extension or PPD
Week (relative to baseline)	24	36	48	60	72
Recommended visit window (days)	±7	±7	± 7	±7	±7
Informed consent	X				
Inclusion/Exclusion criteria	X				
Physical Examination		X	X	X	X
Weight and waist		X	X	X	X
Vital signs		X	X	X	X
PASI		X	X	X	X
IGA mod 2011		X	X	X	X
Lab assessments: hematology and chemistry [†]		X	X	X	X
Urinalysis		X	X	X	X
Secukinumab administration	AS NEEDED				
DLQI			X		X
HADS			X		X
Check self-administration log		X	X	X	X
Dispensing Secukinumab for self-administration at home	X	X	X	X	
Study extension completion					X
Concomitant medication	AS NEEDED				
Adverse events	AS NEEDED				
Liver events	AS NEEDED				

* E0 corresponds to visit at week 24 of the core study (end of study) for patients proceeding to the extension treatment period. The assessments indicated here are in addition to those already scheduled for EOS visit (see table 6-1)

† Hematology: hemoglobin, hematocrit, red blood cell count, white blood cell count with differential (e.g. neutrophils, basophils, eosinophils, monocytes, lymphocytes) and platelet count. Chemistry: albumin, alkaline phosphatase, total bilirubin, calcium, cholesterol, creatinine, CK, GGT, glucose, LDH, potassium, total protein, AST, ALT, sodium, triglycerides, uric acid, hsCRP.

